3.0 STUDY DESIGN

This would be a non-randomized, open label, phase II, modified 2-stage preliminary efficacy study in patients with metastatic melanoma who are considered good candidates, i.e. ECOG <2, Creat <2.0, Bilirubin < 2.0 for a trial of high dose IL-2 treatment. Standard doses and delivery of both the high dose IL-2 and the temozolomide would be utilized. The total accrual goal for the trial would be up to 40 patients given in 2 stages. If no responses are noted in the first 12 patients accrued then the study will be terminated. If there is any response in the first 12 patients (CR, PR

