8.0 DATA ANALYSIS AND STATISTICAL METHOD

8.1 Sample Size Determination

The study will employ a Simon 2-stage optimal design with the following specifications: $p_0 = 0.05$, $p_1 = 0.20$, $\alpha = 0.10$, $\beta = 0.10$, where p_0 is the ineffective response rate, p_1 is the effective response rate, α is the false positive rate, and β is the false negative rate. With these specifications, a 2-stage Simon optimal design, which minimizes the expected sample size given an ineffective response rate, will enroll a total of 37 patients with 12 during stage 1 and 25 during stage 2. If there is no response among the first 12 patients, then the drug is considered ineffective and the enrollment will be stopped. Otherwise, the study will proceed to stage 2. The drug will be considered effective if there are at least 4 responses by the completion of the trial.

The design will assure good statistical power with respect to differentiating response rates of 5% and 20% (12). Three additional patients will be enrolled to allow for dropouts to a total of 40.

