8.2 Efficacy Determination

Efficacy analysis will be performed on the intention-to-treat set, which comprises of all patients enrolled in the trial. Patients must have completed at least one complete course (2 cycles) to be considered for response assessment. Patients receiving less than one course will be considered drop-outs from the study in terms of response. Patients who do complete at least one course of treatment will be classified as responders or non-responders. The overall response rate, which is the proportion of the responses among patients in the intention-to-treat set who have completed at least one complete course, will be obtained. In addition, a 95% confidence interval for the overall response rate will be constructed. Responses will be recorded after each course of therapy and will be tabulated as complete response, partial response, minor response, stable disease or progressive disease. Only PR and CR will be included in the numerator of the analysis for overall response but all responses will be recorded. The time to progression (TTP) in months for each patient will be recorded to ascertain the durability of the responses. Waterfall plots for a continuous assessment of response will also be generated. Correlative science results will be studied by non-parametric methods for differences in a given individual over time and between individuals.

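### The Simon cut-offs for 12 and 37 patients are not tied to assessable patients, so the stated alpha of 0.10 and power of 0.90 are not guaranteed

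*Combined protocol and SAP*

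**What the plan says.** Section 8.1 commits to a Simon design ("The study will employ a Simon 2-stage optimal design with the following specifications") with response rates of 5% and 20% and both error rates at 0.10. The trial "will enroll a total of 37 patients with 12 during stage 1 and 25 during stage 2". The interim rule is: "If there is no response among the first 12 patients, then the drug is considered ineffective and the enrollment will be stopped". The final rule is: "The drug will be considered effective if there are at least 4 responses by the completion of the trial". It gives no denominator. The section closes with: "Three additional patients will be enrolled to allow for dropouts to a total of 40".

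Three other statements bear on who is counted:

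- Section 3.0 reads the interim on accrued patients: "If no responses are noted in the first 12 patients accrued then the study will be terminated". It lets a CR, PR or minor response (MR) open stage 2.
- Section 3.0 also describes the three extra patients as a permitted allowance for early drop-outs (fewer than 2 complete cycles), within a ceiling of 40.
- Section 8.2 states: "Efficacy analysis will be performed on the intention-to-treat set, which comprises of all patients enrolled in the trial". The same paragraph treats patients with less than one course as drop-outs for response, takes the response rate among those who completed at least one course, and puts only CR and PR in the numerator.

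**The concern.** The cut-offs of 0 and 4 control the error rates only for the sample sizes from which they were derived. Nowhere does the plan say that 12 and 37 are counts of assessable patients, or what happens if the counts differ.

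Two departures follow, in opposite directions. If all three extra patients are enrolled and few patients drop out, 39 or 40 assessable patients face a threshold set for 37, and the false-positive rate rises. If drop-outs occupy places among the first 12 accrued, fewer than 12 patients can show the one response needed to continue, so an effective regimen is stopped more often.

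This is the only go/no-go rule in a single-arm, open-label trial. If the denominator is left open, it could be settled after responses are known: a fourth response among patients 38 to 40 could turn a failure into a success.

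**Working it through.** **Inputs (section 8.1).** p0 = 0.05, p1 = 0.20, alpha and beta limits 0.10, n1 = 12, n2 = 25, stop at 0 responses, success at 4 or more.

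**Formula.** With n1 assessable patients in stage 1 and n2 in stage 2,

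P(success | p) = Σ over x = 1..n1 of Bin(x; n1, p) × P(Bin(n2, p) ≥ 4 − x).

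This is alpha at p = 0.05 and power at p = 0.20. The false-stop risk is 0.80^n1. Only CR and PR count, at both looks.

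**Step 1: the plan's own design, 12 + 25.**

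- p = 0.05: 0.3413 × 0.1271 + 0.0988 × 0.3576 + 0.0173 × 0.7226 + 0.0022 (four or more in stage 1) = 0.0434 + 0.0353 + 0.0125 + 0.0022, which is 0.0935 before rounding of terms.
- p = 0.20: 0.1859 + 0.2757 + 0.2353 + 0.2054, which is 0.9024 before rounding.

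A search over all designs meeting both limits returns this one as having the smallest expected sample size under p0 (23.5). Section 8.1 is therefore arithmetically right.

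**Step 2: same rule, other assessable counts.**

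| Assessable, stage 1 + stage 2 | Total | Alpha | Power | False stop at 20% |
|---|---|---|---|---|
| 12 + 25 | 37 | 0.0935 | 0.902 | 6.9% |
| 12 + 26 | 38 | 0.0994 | 0.907 | 6.9% |
| 12 + 27 | 39 | 0.1055 | 0.911 | 6.9% |
| 12 + 28 | 40 | 0.1116 | 0.914 | 6.9% |
| 11 + 26 | 37 | 0.0899 | 0.887 | 8.6% |
| 10 + 27 | 37 | 0.0857 | 0.867 | 10.7% |
| 9 + 28 | 37 | 0.0810 | 0.842 | 13.4% |
| 11 + 28 | 39 | 0.1012 | 0.895 | 8.6% |

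Rows 3 and 4 need zero or one drop-out among 40 enrolled. Rows 5 to 7 have one to three drop-outs in stage 1, replaced later so that 37 are assessable. The last row is 40 enrolled with one drop-out, in stage 1; both limits are then missed slightly.

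Moving the final cut-off does not rescue 40 patients: with 12 + 28, requiring 5 responses gives alpha 0.0417 but power 0.877.

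**Step 3: typical size with exactly three drop-outs.** If they fall at random among 40 enrolled, the chances of 0, 1, 2 or 3 in the first 12 are C(12,k) × C(28,3−k) / C(40,3) = 0.332, 0.459, 0.187 and 0.022. Weighting rows 1, 5, 6 and 7 accordingly gives alpha about 0.090 and power about 0.887.

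**Step 4: effect of letting MR open stage 2 (section 3.0).** With MR probability m, P(success) = P(Bin(n1 + n2, p) ≥ 4) − (1 − p − m)^n1 × P(Bin(n2, p) ≥ 4). The plan gives no value for m, so these are assumptions:

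- m = 2%: power 0.903 at 11 + 26 and 0.887 at 10 + 27.
- m = 5%: power 0.921 and 0.909, with alpha 0.0997 and 0.097. At 12 + 28, alpha is 0.124. At 12 + 25, alpha is 0.1119 − 0.90^12 × 0.0341 = 0.1119 − 0.2824 × 0.0341 = 0.102.

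**The case against.** The strongest reply is that the intent is clear. Section 3.0 presents the extra patients as cover for early drop-outs, within a ceiling of 40, and section 8.1 gives the same purpose. On that reading a trial without drop-outs ends at 37. Section 8.2 takes the response rate only among patients who completed a course, so the all-enrolled set is not simply the denominator. This stands as the likely intent. It is not a rule: section 8.1 says the three will be enrolled, the success criterion has no denominator, and nothing restricts patients 38 to 40 to replacement.

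A second reply is that an MR can open stage 2, which offsets the stage 1 power loss. That is correct as far as it goes: at an assumed 5% MR rate, power stays above 0.90 with one or two stage 1 drop-outs. But the same gate raises alpha, and section 8.1 does not say which responses its gate counts.

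Third, the alpha excess needs at most one drop-out in 40. At an assumed 7.5% rate (3/40) that has probability 0.925^40 + 40 × 0.075 × 0.925^39 = 0.188, and the excess is then only about one point. This also stands, and it limits the importance of the point.

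A reader might infer that the sample-size calculation is wrong, or that the plan fails both its alpha and its power. The documents support neither. The design reproduces exactly, and both limits hold at 12 + 25 and 12 + 26. In most other cases only one limit fails; 11 + 28 misses both, by 0.001 in alpha and 0.005 in power.

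**Conclusion.** The point holds in conditional form. The cut-offs are right for 12 and 37 assessable patients, but the text does not tie them to such patients, so the stated limits are not guaranteed. With CR and PR only and 12 assessable in stage 1, alpha can reach 0.1116 against a limit of 0.10. With drop-outs in stage 1 replaced up to 37, power is 0.842 to 0.887 against 0.90. With three drop-outs placed at random, the average loss is about 1.5 points from the design's 0.902.

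These figures assume independent responses and drop-out unrelated to response. If drop-outs are instead kept as non-responders among 40 enrolled, an assumed 7.5% rate gives alpha 0.090 and power 0.886. The effect is modest, but it concerns the trial's sole decision rule and can be removed before any data are seen.

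**What to change.** In sections 3.0 and 8.1, state that both cut-offs apply to one named set, the response-assessable set of section 8.2 (patients completing at least one course): 0 of the first 12 and at least 4 of the first 37, by enrolment order. State that patients 38 to 40 are entered only to replace drop-outs and otherwise do not count toward the decision; they can appear in a supplementary estimate.

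Two clarifications are needed for this to work:

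- Use one definition of drop-out. Section 3.0 counts cycles and section 8.2 counts courses, and elsewhere a course includes the temozolomide period.
- State which responses open stage 2. The figures of 0.0935 and 0.902 assume CR and PR only; if MR also counts, both should be recalculated.

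If all 40 are meant to count, say so. State that with no drop-outs and a CR/PR gate alpha is 0.112 and power 0.914, and that both change with the number and timing of drop-outs.

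The cost is protocol wording. Up to three enrolled patients may not count toward the go/no-go decision, and stage 1 may need slightly more than 12 accrued.

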8.2 Efficacy Determination

Efficacy analysis will be performed on the intention-to-treat set, which comprises of all patients enrolled in the trial. Patients must have completed at least one complete course (2 cycles) to be considered for response assessment. Patients receiving less than one course will be considered drop-outs from the study in terms of response. Patients who do complete at least one course of treatment will be classified as responders or non-responders. The overall response rate, which is the proportion of the responses among patients in the intention-to-treat set who have completed at least one complete course, will be obtained. In addition, a 95% confidence interval for the overall response rate will be constructed. Responses will be recorded after each course of therapy and will be tabulated as complete response, partial response, minor response, stable disease or progressive disease. Only PR and CR will be included in the numerator of the analysis for overall response but all responses will be recorded. The time to progression (TTP) in months for each patient will be recorded to ascertain the durability of the responses. Waterfall plots for a continuous assessment of response will also be generated. Correlative science results will be studied by non-parametric methods for differences in a given individual over time and between individuals.

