progression for at least eight weeks at the time of enrollment. Patients must not require corticosteroids for treatment of cerebral edema for brain metastases. Patients must be evaluated with a head MRI within 4 weeks prior to enrollment. Patients may have had prior dacarbazine or temozolomide since the mechanism of action of the temozolomide to be used in the context of this study is related more to effects on immune cells than to its known anti-melanoma effects. Patients would receive baseline staging imaging and laboratory assessment including study-specific immunologic correlative science testing. Patients would receive HD IL-2 according to standard procedure as in-patients on the PSHCI inpatient clinical unit. Patients would receive Cycle 1 of aldesleukin at 600,000 International Units/kg every 8 hours as tolerated up to a maximum of 14 doses. On or about day 10 after discharge from Cycle 1, they would be re-admitted for Cycle 2 of treatment. Then, 28 days after discharge from Cycle 2, they would receive temozolomide at 75 mg/m² daily for 21 days. Two cycles of HD IL-2 therapy as performed above plus 21 days of temozolomide would constitute one course of therapy. After this they would be scanned to assess response with CT/PET or CT(CAP). Responding patients (CR, PR, SD, Minor Response) would be given a 2nd course of treatment as above. Patients with a CR would receive one additional course of treatment and would then be observed. Patients with SD after 2nd course of treatment would go off study. Patients with a PR or Minor Response would continue treatment up to a maximum of 4 courses (8 cycles). If they develop Progressive Disease at any time during this treatment then they would go off study. If they develop a CR then they would have one additional course of treatment provided this course does not make more than 4 total courses. If they have PR or Minor Response after Course 2 then they would receive up to 2 additional courses.

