or MR) then accrual of an additional 25 patients will ensue. Three additional patients would be allowed to accrue to cover any early drop-outs (receipt of less than 2 complete cycles of treatment). Eligible patients would have baseline imaging with CT or CT/PET. A head MRI to rule out asymptomatic occult brain metastases will be performed on all patients as well. Patients with known brain metastases will have baseline MRI done as well and would then have follow-up MRIs performed after each course. An echocardiogram to check cardiac function and PFTs with DLCO will be performed in all patients to assure that they have adequate cardiopulmonary reserve to sustain HD IL-2 as is standard. Patients would have baseline laboratory testing done pre-treatment and at every cycle initiation. An autoimmune panel will be performed pre-treatment and after every cycle of treatment. Correlative science immunoassays will be performed pre-treatment and after every cycle of treatment. Response as per radiologic imaging assessment and physical assessment of accessible and measurable skin metastases if applicable will be performed after every course of treatment (2 cycles HD IL-2 and 21 days of temozolomide.). Response will be determined after course 1 of treatment as a complete response (CR), partial response (PR), minor response (MR), stable disease (SD) or progressive disease (PD) according to standard definitions of response. Patients with CR will receive another complete course of treatment and will then go off study except for follow-up. Patients with progressive disease (PD) will go off study after course 1. Patients with stable disease (SD) after course one will repeat one additional course maximum. Patients with PR or MR will continue with additional courses as determined by response up to a maximum of 4 courses total (8 cycles). Responses and their durability will be compared to known rates of response and their durability using HD IL-2 alone. For a population of 40, using standard HD IL-2, the expected response rate 10% would be in 4 of the 40 and the CR rate 5% in about 2 of the 40. We would hypothesize that we can at least double these at a minimum using the methods described in this protocol.

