² – Patients with or without known brain metastases can get an MRI at any time, should they develop neurological Symptoms as determined by the investigator

³ – Will include ESR, CRP, ANA, RF and TSH

⁴ – Will include flow cytometry, Elispot, flow- based tetramer analysis (To be processed by [name]'s lab [name])

⁵ CBC, diff, platelets, CMP, LDH,

⁶ – This scheme will be repeated up to 4 courses

⁷ – CRP only

⁸ - Post-cycle labs will be drawn 24-72 hours after completion of the last dose of IL-2 for each cycle. These may be obtained while the patient is admitted, as long as it falls within the 24-72 hour timeframe and has been arranged with the study coordinator.

One Course is comprised of 2 cycles of high dose IL-2 followed by 4 weeks off, then 3 weeks of continuous low dose oral temozolomide, with another 2 weeks off prior to reimaging (approximately 12 weeks in duration from start to finish)

Study Schema Algorithm: Phase II Trial of High Dose Interleukin-2 followed by intermittent low dose Temozolomide in patients with Metastatic Malignant Melanoma

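### Section 8.2 admits patients to the response rate by completion of a course, but a course has two meanings, so patients who stop after IL-2 Cycle 2 and before temozolomide ends may be kept or removed

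*Combined protocol and SAP*

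**What the plan says.** **The entry condition.** Section 8.2 states "Patients must have completed at least one complete course (2 cycles) to be considered for response assessment" and, next, "Patients receiving less than one course will be considered drop-outs from the study in terms of response". Two further sentences of 8.2 depend on the same unit without repeating the gloss. One says that patients who complete a course are classified as responders or non-responders. The other makes course completers the denominator of the overall response rate.

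**The drop-out allowance.** Section 3.0 says "Three additional patients would be allowed to accrue to cover any early drop-outs (receipt of less than 2 complete cycles of treatment"). Section 8.1 also adds three patients for drop-outs, to a total of 40, without defining the term.

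**The definition of a course.** Section 1.3: "Two cycles of HD IL-2 therapy as performed above plus 21 days of temozolomide would constitute one course of therapy". Sections 3.0 and 6.1 include temozolomide in the same way. The flow chart in the appendix agrees: "One Course is comprised of 2 cycles of high dose IL-2 followed by 4 weeks off, then 3 weeks of continuous low dose oral temozolomide".

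**The design.** Under section 8.1 the trial "will enroll a total of 37 patients with 12 during stage 1 and 25 during stage 2". The stage 1 rule is "If there is no response among the first 12 patients, then the drug is considered ineffective and the enrollment will be stopped", and success is at least 4 responses at the end.

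**The concern.** Take a patient who completes IL-2 Cycle 2 and then stops during the 28-day gap or the 21 days of temozolomide. If a course means two IL-2 cycles, the patient is assessable. Response imaging is scheduled only after temozolomide, so the patient would normally be scored a non-responder. If a course includes temozolomide, the same patient has had less than one course and leaves the denominator.

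Two careful analysts could therefore report different primary rates from the same data. The patients at issue are not a random subset: deaths, symptomatic progression and toxicity withdrawals in those seven weeks are mostly treatment failures, so removing them can only raise the rate.

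Replacement is affected too. Section 3.0 would not treat this patient as an early drop-out, 8.2 read with the full course definition would, and 8.1 does not say. The composition of the first 12 patients, on whom the stage 1 decision rests, depends on the same unit.

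**Working it through.** **Inputs.** From 8.1: p0 = 0.05, p1 = 0.20, alpha = 0.10, beta = 0.10; 12 + 25 = 37 patients; stop at 0 of 12; success at 4 or more; 3 extra patients, total 40. From 4.2.1: temozolomide starts 28 days after Cycle 2 discharge and lasts 21 days, so the window is 28 + 21 = 49 days. From 5.3: imaging about 14 days after the last dose. The documents give no expected stopping rate, so every stopping fraction below is an assumption.

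**Step 1: reproduce the design.** P(success | p) = sum over x = 1 to 12 of Bin(x; 12, p) × P[Bin(25, p) ≥ 4 − x].

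- p = 0.05: 0.0935
- p = 0.20: 0.9024

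A grid search for the optimal design at these specifications returns the same 12/37 design. The plan's figure stands.

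**Step 2: the same patient under each reading** (both IL-2 cycles received, stopped before temozolomide ended).

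| Text | In the denominator? | Replaceable? |
|---|---|---|
| 3.0 drop-out rule | Not addressed | No |
| 8.2 with its two-cycle gloss | Yes, normally as non-responder | Not addressed |
| 8.2 with the course definition of 1.3, 3.0, 6.1 and the flow chart | No | Not addressed, but labelled a drop-out |
| 8.1 | Not addressed | Yes, if a drop-out |

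**Step 3: effect on the reported rate.** With 4 responders:

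- Stoppers kept: 4/37 = 10.8% (exact 95% CI 3.0 to 25.4%)
- 3 removed: 4/34 = 11.8% (3.3 to 27.5%)

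The 3 is an assumption. For scale, exponential survival with a 12-month median (section 1.1 says less than one year) gives 1 − exp(−ln 2 × 1.61/12) = 8.9% dying in 49 days (1.61 months), and 37 × 0.089 = 3.3 patients.

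**Step 4: effect on the false-positive rate if removed patients are replaced.** Let a fraction d stop in the window, be unable to respond, and be replaced until 37 are assessable. If the response rate in all patients is 5%, the rate among those retained is 0.05/(1 − d).

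| d | Rate among retained | P(success) | Enrolment needed, 37/(1 − d) |
|---|---|---|---|
| 0 | 5.00% | 0.0935 | 37 |
| 5% | 5.26% | 0.107 | 39 |
| 10% | 5.56% | 0.124 | 42 |
| 20% | 6.25% | 0.167 | 47 |

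The last two rows need more than the 40 patients allowed; three extra patients cover only 3/40 = 7.5%. Holding enrolment at 40 and using the same formula with n = 40 × (1 − d):

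- d = 7.5%: 37 assessable, rate 0.05/0.925 = 5.41%, P(success) 0.115
- d = 10%: 36 assessable, 0.117
- d = 20%: 32 assessable, 0.122

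For comparison, counting all 40 against the threshold of 4 gives 0.112. The excess arises largely because more patients are drawn against a fixed count.

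**Step 5: without replacement.** Removing patients who have no response does not change the number of responses among the 37 enrolled. The final decision is then the same on both readings; the reported rate, its interval and the make-up of the first 12 differ.

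**The case against.** The best defence is that the two drop-out rules can be harmonised. The gloss in 8.2 agrees with 3.0, and the phrase in 1.3 and 3.0 that equates four courses with eight cycles counts IL-2 cycles only. On this view, two IL-2 cycles was always meant. This stands in part: the split lies in the word course within 8.2 more than between 3.0 and 8.2. It does not settle the matter. The denominator sentence carries no gloss, four places define a course as including temozolomide, and cycle is not stable either: 5.3 counts four cycles of temozolomide alongside eight of IL-2.

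Three stronger readings are tempting and are not supported.

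- **Loss of power.** A reader might infer that removal costs the 90% power. With 20% response among assessable patients, removing 3, 7 or 10 of 37 without replacement gives 0.884, 0.843 and 0.794. Under the same assumption, keeping them as non-responders gives 0.867, 0.800 and 0.733. If 20% is instead the all-patient rate, removal gives 0.918 at n = 34 and 0.948 at n = 27. Power does not favour either reading.
- **Very large exclusions.** The 3.3-month median time to progression cited in 1.2 would put 1 − exp(−ln 2 × 1.61/3.3) = 29% progressing in the window. With scheduled imaging only after temozolomide, most of that progression would be found at the post-course scan, in a patient who had completed the course.
- **Section 3.0 calls them non-responders.** It does not. That follows from the classification in 8.2 and the timing of imaging.

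Finally, 8.2 also names an all-enrolled intention-to-treat set. If that became the denominator, the rate effect would disappear and only the replacement question would remain. While a completer denominator is kept, completer has two meanings.

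**Conclusion.** The concern holds as an unresolved ambiguity in who enters the primary response rate and who may be replaced. Its effect on the estimate is modest on plausible assumptions: 10.8% against 11.8% with 4 responders and 3 patients removed. Its effect on the error rate appears only if removed patients are replaced: 0.107, 0.124 or 0.167 at assumed 5%, 10% or 20% stopping, or about 0.12 at 10% to 20% stopping when enrolment is held at 40, against the stated 0.10. These figures assume that stoppers cannot respond and that 5% is the rate in all patients; if 5% is meant among assessable patients only, there is no inflation. The sample size of 37 is correct. The point should be fixed because the direction of bias is known and the ambiguity touches the stage 1 decision, not because power is lost.

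**What to change.** Use one evaluability unit in 3.0, 8.1 and every sentence of 8.2, including the sentence that classifies course completers and the one that defines the denominator. Suggested unit: *both IL-2 cycles of course 1, whether or not temozolomide was started or completed*.

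Add: *A patient who received both IL-2 cycles but has no post-course-1 response assessment, for any reason including death, is a non-responder and is not replaced. The same rule applies to the 12-patient stage 1 decision.*

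Report separately how many counted responders received no temozolomide, since the primary objective concerns the sequence of the two drugs.

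This changes analysis wording only; it needs no new data or patients and alters no treatment rule. The cost is that the reported response rate can only be equal or lower for patients who stop early without a response.

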5.3 Therapy

After baseline studies have been completed, the patients would be admitted to the PSHCI inpatient clinical unit for Course 1 Cycle 1 of HD IL-2 treatment. Treatment will proceed according to the standard treatment algorithm utilized by the PSHCI inpatient clinical unit. Patients will be given as many doses of IL-2 up to a maximum of 14 at 8 hr intervals as allowed by the algorithm at 600,000 International Units/kg. Patients will receive standard supportive measures including fluid boluses, antiemetics and antipyretics as indicated. The patients will be discharged when the acute toxicities of the IL-2 have subsided. They will be reassessed on or about Day 10 after discharge from Cycle 1 and will be re-admitted for Cycle 2. After Cycle 2 of HD IL-2, they would begin temozolomide at 75 mg/m² on the 28th day after discharge and they would take it daily at bedtime for 21 days. Approximately 14 days after the final dose of temozolomide, patients will be assessed for response via imaging. The response determined after restaging post course 1 would determine the next step. Patients with progressive disease would go off study. Patients with a CR would receive one additional course of treatment and would then be observed. Patients with SD would receive one additional course of treatment. Patients with a PR or minor response would continue treatment up to a maximum of 4 courses (8 cycles HD IL-2 and 4 cycles of temozolomide). If they develop progressive disease at any time during this treatment then they would go off study. If they develop a CR then they would have one additional course of treatment provided this course does not make more than 4 total courses. If they have PR or minor response after course 2 then they would receive up to 2 additional courses.

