5.5 Removal of Patients from Therapy

Patients can remove themselves from the study at any time for any reason. Patients will be removed from the study by an investigator for undue toxicity as determined by an investigator. Patients will also be removed if they demonstrate disease progression or stable disease as defined above.

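### Section 8.2 declares an all-enrolled intention-to-treat set but computes the response rate and its 95% CI over course completers only, so the reported rate can only equal or exceed the intention-to-treat rate

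*Combined protocol and SAP*

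**What the plan says.** The conflict lies within one paragraph of section 8.2. It opens with the analysis set: "Efficacy analysis will be performed on the intention-to-treat set, which comprises of all patients enrolled in the trial". It then sets a condition, "Patients must have completed at least one complete course (2 cycles) to be considered for response assessment", and a consequence, "Patients receiving less than one course will be considered drop-outs from the study in terms of response". Only patients who finish a course are classified as responders or non-responders. The overall response rate is "the proportion of the responses among patients in the intention-to-treat set who have completed at least one complete course", with CR and PR in the numerator, and the 95% CI is for that rate. No section plans a rate over all enrolled patients.

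Section 5.5 gives the routes by which a patient may leave early: "Patients can remove themselves from the study at any time for any reason", and "Patients will be removed from the study by an investigator for undue toxicity as determined by an investigator". It also says "Patients will also be removed if they demonstrate disease progression or stable disease as defined above", without tying this to a particular course.

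The documents do not agree on what a completed course is:

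- Section 8.2 glosses it as 2 cycles, and section 3.0 defines early drop-out as fewer than 2 complete cycles.
- Section 1.3 adds 21 days of temozolomide.
- Section 6.1 and the note under the Time and Events Schedule also add the rest periods up to reimaging, about 12 weeks in all.

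**The concern.** Clinical response is the first primary objective (2.1), and section 3.0 compares the observed responses with known rates for high-dose IL-2 alone. The plan names one population for this estimate and calculates it on another.

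The exclusion is unlikely to be neutral. Patients who stop for toxicity, withdraw, die, or progress clinically before the post-course scan are mostly treatment failures. Under intention-to-treat they would count as non-responders; under 8.2 they are not counted at all. A rate and CI reported under the intention-to-treat label would therefore be completer-only. The unsettled definition of a course also leaves open who is excluded, and that could be decided after outcomes are known.

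**Working it through.** **Inputs.** From 8.1: p0 = 0.05, p1 = 0.20, alpha = beta = 0.10; 12 + 25 = 37 patients; stop at 0/12; effective if at least 4 responses; 3 more patients for drop-outs, total 40. From 8.2: numerator CR + PR, denominator completers, 95% CI. Section 8.2 names no CI method, so Clopper-Pearson is assumed.

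**1. Reproduce the design.** With X1 ~ Bin(12, p) and X2 ~ Bin(25, p), P(declare effective) = P(X1 ≥ 1 and X1 + X2 ≥ 4).

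- At p = 0.05: 0.0935. At p = 0.20: 0.9024.
- P(early stop at p0) = 0.95^12 = 0.540. Expected N = 12 + 25 × (1 − 0.540) = 23.5.
- An exhaustive search for the smallest expected N under these limits returns the same design, so 8.1 is internally correct.

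**2. Ratio of the two rates.** Let x be the responders, N the enrolled and m the drop-outs. Because 8.2 credits no drop-out with a response, both rates have numerator x:

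(x/(N − m)) / (x/N) = N/(N − m) = 1/(1 − d), with d = m/N.

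This is never below 1, and the two rates differ whenever m ≥ 1 and x ≥ 1.

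- d = 3/40 = 0.075 (documented allowance): 40/37 = 1.08
- d = 0.10 (assumed): 1.11
- d = 0.20 (assumed): 1.25

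**3. Size on the rate and CI.**

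| Responses | All 40 enrolled | 37 completers | Shift (points) |
|---|---|---|---|
| 4 | 10.0% (2.8 to 23.7) | 10.8% (3.0 to 25.4) | 0.8 |
| 6 | 15.0% (5.7 to 29.8) | 16.2% (6.2 to 32.0) | 1.2 |
| 8 | 20.0% (9.1 to 35.6) | 21.6% (9.8 to 38.2) | 1.6 |

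The intervals for 6 and 8 responses are 24.1 to 28.4 points wide. With an assumed 8 drop-outs, 8/40 = 20.0% would be reported as 8/32 = 25.0% (11.5 to 43.4).

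**4. How often the rates differ.** With 40 enrolled, drop-out probability d and all-enrolled response probability p, P(at least one of each) = 1 − (1 − d)^40 − (1 − p)^40 + (1 − d − p)^40. At d = 0.075 this is 0.83, 0.94 and 0.96 for p = 0.05, 0.10 and 0.20.

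**5. Decision rule.** Section 8.1 does not say whether the 12 and 37 are enrolled or completing patients. At d = 0.075:

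- *Rules run on 37 completers, drop-outs replaced.* An all-enrolled rate of 5% is a completer rate of 0.05/0.925 = 0.054. The false-positive probability is 0.115, against 0.093 in step 1 and the 0.10 limit.
- *Rules run on 37 enrolled, the 20% target meant for completers, non-completers not responding.* The all-enrolled rate is 0.20 × 0.925 = 0.185. Power is 87.0%, against 90.2%.

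**The case against.** The denominator is written out in the defining sentence, so a careful reader of 8.2 is not misled. A design of 37 plus 3 looks like an evaluable-patient design, and relabelling the set would also remove the contradiction. These points have weight: which rate leads the report is partly a matter of choice. Relabelling alone, however, would still leave no all-enrolled rate.

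The exclusion may also be narrow. On the 2-cycle reading it covers only two admissions, the second on or about day 10 after discharge from the first. The IL-2 mortality of below 2% in 4.1.2 is fewer than 0.8 of a patient in 40. Time to progression is recorded for each patient (8.2) and off-study patients are followed for progression and survival (5.6), so early failures remain visible there. All this stands, and limits the size.

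A reader might infer from 5.3 that patients progressing in course 1 generally leave the denominator, since it says "If they develop progressive disease at any time during this treatment then they would go off study". The documents do not support that. The sentence follows the one about PR and minor-response patients continuing to later courses. Sections 3.0 and 5.3 tie the course 1 decision to the post-course assessment, and the schedule places body imaging only at baseline and post course. Patients whose progression is found at that scan stay in as non-responders. Only clinical progression before it can remove a patient.

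**Conclusion.** The inconsistency is certain from the text and should be fixed; its documented size is modest. The completer rate equals or exceeds the all-enrolled rate under 8.2's own rules, by a factor of 1.08 at the 3/40 allowance, or 0.8 to 1.6 points for 4 to 8 responses. Anything larger rests on an assumed drop-out share. The intervals rest on the assumed exact method.

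Two stronger conclusions might be inferred and do not follow. One is that the go/no-go decision is compromised: the rule is a count of at least 4, and leaving drop-outs out of a denominator does not change a count. Its false-positive probability rises only if drop-outs are replaced so that it runs on 37 completers, which the documents neither state nor rule out. The other is that the comparison with historical IL-2 rates is biased by a known amount: the documents do not give the denominator behind those rates. The supported point is that the all-enrolled rate should be available for that comparison.

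**What to change.** - **8.2, primary rate.** Compute the intention-to-treat response rate and its 95% CI as CR + PR over all enrolled patients. Count patients with no documented CR or PR as non-responders, including those with no post-baseline assessment. Keep any response documented on study, in line with the best-response rule in 6.1, so that a responder who later withdraws is not reclassified. Name the CI method.
- **8.2, second rate.** Report the completer rate beside it, labelled completer-only.
- **1.3, 3.0, 6.1, 8.2 and the note under the Time and Events Schedule.** Use one definition of completed course and of drop-out for evaluability. This concerns who is counted, not treatment.
- **8.1.** Leave the 0/12 and at-least-4 rules unchanged. State whether the 12 and 37 are enrolled or completing patients, which population p0 and p1 describe, and the resulting error rates (step 5 of the working gives both cases at 7.5% drop-out).

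The cost is wording only, with no new patients or data. The downside is a slightly lower headline rate and, if the rules run on enrolled patients with a completer-based 20% target, an open statement that power is 87.0% at that allowance rather than the planned 90%.
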